 At each time point, growth measurements (recumbent length or height, weight and head circumference) will be measured 3 times in a row and averaged. All measurements should be recorded to the nearest tenth of a centimeter. The measurement of recumbent length or height, weight and head circumference should be performed by an individual, who does not have access to the records of the patient's earlier measurements in the study and, as far as possible, by the same individual at each patient visit.

 Bayley-III is to be discontinued when the patient reaches 42 months of age. The Bayley-III will be administered to patients from 1 month of age until the maximum score on each of the 3 administered scales has been obtained. Once the maximum score for a scale has been achieved, only the remaining scales will be administered.

 Additional anti-alglucosidase alfa IgG antibody testing should be performed upon determination of any notable deterioration in a patient's motor function.

 Modified Leiter-R Scale or updated Leiter-3 Scale assessment is to be performed at the last assessment of the Bayley-III Cognitive and Language Scales prior to the patient reaching 42 months of age and annually thereafter until the patient reaches the end of the follow up period. If previous assessments have been performed using Leiter-R and switch to Leiter-3 Scale is planned, then both assessments need to be performed at the same time of the initial administration of the Leiter-3, in order to create a baseline. The dates of the two tests should be recorded appropriately in the CRFs and the scores recorded on the appropriate test score sheets.

 Oligosaccharide (Hex4) testing will be performed every 6 months until the 24th month and then yearly.

 Genzyme Corporation or their designee will perform the CRIM analysis in skin biopsies. CRIM will be conducted only if written results are not available.

 GAA mutation analysis is to be conducted only if written results are not available.

 To be collected every 3 months up to Study Month 24 (3, 6, 9, 12, 15, 18, 21 and 24) and annually thereafter. Additional testing should be performed upon determination of any notable deterioration in a patient's motor function. Serum IgG samples should always be collected pre-infusion at each time point.

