4 STATISTICAL ANALYSES

4.1 GENERAL CONSIDERATIONS

In general, continuous data will be summarized using the number of observations available, mean, standard deviation (SD), median, minimum, and maximum. Categorical and ordinal data will be summarized using the counts and percentages of patients.

The baseline value is defined as the value measured at the Screening/Baseline visit prior to the first infusion during this study. In cases where a patient has more than one value measured during Screening/Baseline, the latest value will be the one used as baseline.

Unless otherwise specified, analyses will be performed for Full Analysis Set (FAS).

Observation period

The observation period will be divided into 2 segments:

- The **pre-treatment period** is defined as the period up to first IMP administration (ie, when the patients started receiving the alglucosidase alfa in the study, even if the patient had received alglucosidase alfa prior to entering the study).
- The **on-treatment period** (ie, treatment-emergent (TE) period) is defined as the period from the first IMP administration in the study to the last study assessment.

The on-study period is defined as the time from the signing of the informed consent until the end of the study (defined as the completion date or the discontinuation date collected on the case report form (CRF) page “Completion/Discontinuation”).

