4.7.2 Adverse events

General common rules for adverse events

All adverse events (AEs) will be coded to a lower-level term (LLT), preferred term (PT), high-level term (HLT), high-level group term (HLGT), and associated primary system organ class (SOC) using the Medical Dictionary for Regulatory Activities (MedDRA) version in effect at Sanofi at the time of database lock.

The AEs will be analyzed in the following 2 categories:

- Pre-treatment AEs: AEs that developed, worsened, or became serious during the pre-treatment period.
- Treatment-emergent adverse events (TEAE)s: AEs that developed, worsened, or became serious during the treatment-emergent period

Deaths during the study period will be provided in a listing.

The primary focus of AE reporting will be on TEAEs. Pre-treatment AEs will be described separately.

An AE with incomplete or missing date/time of onset (occurrence, worsening, or becoming serious) will be classified as a TEAE unless there is definitive information to categorize it as a pre-treatment or a post-treatment AE.

If the assessment of the relationship to IMP is missing for an AE, this AE will be assumed as related to IMP. If the severity is missing for 1 of the treatment-emergent occurrences of an AE, the severity will be imputed with the maximal severity of the other occurrences. If the severity is missing for all the occurrences, the severity will be left as missing.

Multiple occurrences of the same event in the same patient will be counted only once in the tables within a treatment phase.

The AE tables will be sorted as indicated in [Table 4](#).

Table 4 - Sorting of AE tables

AE presentation	Sorting rules
SOC and PT	By the internationally agreed SOC order and decreasing frequency of PTs ^{a, b}

a Sorting will be based on the overall number of patients.

b The table of all TEAEs presented by SOC and PT will define the presentation order for all other tables (eg, treatment-emergent SAE) presented by SOC and PT, unless otherwise specified.

Analysis of all adverse events

The overview of TEAE with event count and number (%) of patients will be generated:

- Any AE
- Any TEAE
 - TEAE related to the study drug
 - TEAE unrelated to the study drug
- TEAEs by severity (mild, moderate, severe)
- TEAEs by gender
- Any treatment emergent SAE
- Any treatment emergent SAE considered related to study drug
- Any protocol-defined infusion-associated reactions
- Any TEAE leading to treatment adjusted

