- Any TEAE leading to treatment interrupted
- Any TEAE leading to permanent intervention discontinuation
- TEAE leading to death

The AE summaries of [Table 5](#) will be generated with event count and number (%) of patients experiencing at least one event.

Table 5 - Analyses of adverse events

Type of AE	MedDRA levels
All TEAEs	Primary SOC and PT
TEAEs related to IMP	Primary SOC and PT
TEAEs by maximal severity	Primary SOC and PT
Related TEAEs by maximal severity	Primary SOC and PT
Treatment emergent SAEs	Primary SOC and PT
Treatment emergent SAEs related to IMP	Primary SOC and PT
TEAEs leading to permanent intervention discontinuation	Primary SOC and PT
TEAEs leading to death (death as an outcome of the AE as reported by the Investigator in the AE page)	Primary SOC and PT
Pretreatment AE	Primary SOC and PT

Subgroup analysis

TEAEs stratified by the following categories will also be presented by primary SOC and PT:

- Status of high ADA response (with, without)
- Seroconversion status (negative, positive) and peak ADA categories for those who seroconverted

Analysis of deaths

A listing of patients who died during the study will be provided.

Analysis of infusion-associated reactions (IARs) and other AEs of interest

Protocol-defined IARs

Infusion-associated reactions (IARs) are defined as AEs that occur during the infusion or within up to 24 hours after the start of infusion and are considered as related or possibly related to the ERT by the Investigator or the Sponsor. At the discretion of the Investigator, AEs occurring ≥ 24 hours after the start of the infusion that are assessed as related may also be considered IARs.

Algorithm-defined IARs

An alternative definition of IAR which does not rely on the investigators' assessments of an AE's relationship to the treatment will also be employed. It includes potential IARs (all AEs occurring during an infusion or within 2 hours after the completion of an infusion; and all AEs occurring from >2 to 24 hours after the completion of an infusion).

Protocol-defined infusion-associated reactions and algorithm-defined potential IARs will be selected for analyses as indicated in [Table 6](#). Number of events and number (%) of patients experiencing at least one event will be provided for each event of interest for the IARs. Tables will be sorted as indicated in [Table 4](#).

Anaphylactic/hypersensitivity reactions and immune-mediated reactions

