4.8 OTHER ANALYSES

4.8.1 *Immunogenicity analyses*

Anti-rhGAA IgG Binding Antibody

Participant's ADA status, response variable, and kinetics of ADA responses (see definitions below) will be summarized for all patients with available ADA data.

Kinetics of ADA response

Kinetics of ADA response will be derived for patients ever ADA positive, whether with ADA already present at baseline or seroconverted during the study. Time to ADA onset (seroconversion) and time from seroconversion to first peak titer will be described with mean, SD, median, Q1, Q3, minimum, and maximum statistics.

- **Persistent ADA response** is defined as ADA positive at the last sample timepoint and meets one of the following two criteria:
 - ADA positive at two or more sampling time points post baseline, where the first and the last ADA-positive post-baseline samples (irrespective of any negative sample in between) are separated by at least 16 weeks; or
 - ADA positive at last two sampling time points, irrespective of the time in between.
- **High ADA response** is a subcategory of persistent ADA response and identifies a patient who was persistently seropositive positive, had a peak titer ≥ 12800 , and was seropositive at final assessment.
- **Tolerized ADA response** is a subcategory of persistent ADA response and identifies a patient who was persistently seropositive, but seronegative at the final assessment.

The following definitions will also be used:

- **ADA peak titer** (highest ADA titer from first study infusion of alglucosidase alfa) for ever positive patients.
- **Time to ADA seroconversion from first alglucosidase alfa infusion in study**

Time to seroconversion (days) from 1st alglucosidase alfa infusion in study will be calculated by (date of seroconversion - date of 1st alglucosidase alfa infusion in study + 1)

- **Time to first alglucosidase alfa ADA peak titer from seroconversion**

Time to first peak titer (weeks) from seroconversion will be calculated by (date of first peak titer - date of seroconversion + 1) / 7

- **ADA peak titer category** (always negative, 100-800, 1600-6400, ≥ 12800).
- **Last ADA titer** (final assessment after first study infusion of alglucosidase alfa) for ever positive patients.
- **ADA last titer category** (≤ 800 , 1600-6400, ≥ 12800).

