5.2 APPENDIX 2 CHANGES TO PROTOCOL-PLANNED ANALYSES

Regarding the calculation of z-scores for physical growth (recumbent length/height, weight, head circumference) the protocol referred to Center for Disease Control (CDC) Growth Charts. However, the CDC website recommended the World Health Organization (WHO) growth charts for children <24 months of age. If possible, we will incorporate this recommendation. In addition, percentiles of these measurements will be calculated as well.

It was planned to use longitudinal repeated measures modeling to analyze trends in key growth and development parameters over time; however, as out of the 12 patients enrolled 7 patients had withdrawn or died in less than 4 years, this analysis is not likely to be informative and will be omitted.

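### Adverse-event tables by antibody category use whole-study labels without patient-years, so column differences mix antibody level with length of follow-up

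*SAP*

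**What the plan says.** - **Stratifiers (SAP 4.7.2, Subgroup analysis).** TEAEs are shown by system organ class and preferred term, split by high ADA response (with or without) and by "Seroconversion status (negative, positive) and peak ADA categories for those who seroconverted".
- **Metric (SAP 4.7.2, Table 5).** The AE summaries are produced "with event count and number (%) of patients experiencing at least one event". The subgroup paragraph names no metric of its own, and I read it as following this one. No patient-year denominator appears anywhere in the SAP.
- **Labels (SAP 4.8.1).** Peak titer is the "highest ADA titer from first study infusion of alglucosidase alfa". A high ADA responder is a patient who was persistently positive, reached a peak of at least 12800 "and was seropositive at final assessment".
- **Counting period (SAP 4.1).** The on-treatment period, in which TEAEs are counted, "is defined as the period from the first IMP administration in the study to the last study assessment".
- **Counting rule (SAP 4.7.2).** "Multiple occurrences of the same event in the same patient will be counted only once in the tables within a treatment phase".
- **Follow-up.** Protocol Section 5 plans 10 years. SAP 5.2 reports that "out of the 12 patients enrolled 7 patients had withdrawn or died in less than 4 years".
- **Sampling (Protocol Table 9-1, footnote 10).** IgG is "To be collected every 3 months up to Study Month 24 (3, 6, 9, 12, 15, 18, 21 and 24) and annually thereafter", and Protocol 9.1 allows 60 days either side of each visit.
- **Related outputs.** SAP 4.7 states that safety analyses are descriptive and untested. Exposure is listed per patient (SAP 4.7.1), individual titers are plotted over time (SAP 4.8.1), and all AEs are listed (Protocol Section 11).

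**The concern.** Each label is attached to a patient and can be settled only once follow-up has ended. The TEAEs beneath it come from the whole on-treatment period. Neither document ties the onset date of an event to the date of a titer. Three consequences follow.

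1. **Follow-up.** A column that happens to hold more long-stayers collects more events at the same underlying rate.
2. **Time order.** If a patient first reaches 12800 during the study, TEAEs that began before that sample still appear in the 12800-or-more column.
3. **Final sample.** A patient with titers of 12800 or more who is negative at the last sample goes to 'without' in the high-ADA table, together with any events that occurred while the titer was high.

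I found no other planned summary in the SAP that sets ADA against a clinical outcome. A reader who compares 'with' and 'without' could see an association where none exists, or miss a real one.

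**Working it through.** The plan gives no figure to reproduce: there is no sample size, error rate or effect size here. What follows checks direction and possible size. The documents do not give the number of high-ADA patients, individual follow-up times, event rates or the date of the first high sample, so all of these are assumed.

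**1. Unequal follow-up, no ADA effect**

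From the documents: 12 patients, 7 with under 4 years, 10 years (120 months) planned.

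Assumed: the other 5 complete 120 months. The 7 early leavers each have f months, with f = 47 (the longest whole month below 4 years) or f = 24. Four patients are high-ADA, of whom k are long-stayers. The event rate is constant and every episode is counted.

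The ratio of TEAEs per patient, high versus other, is

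[(120k + f(4 − k))/4] ÷ [(120(5 − k) + f(3 + k))/8]

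| k | f = 47 | f = 24 |
|---|---|---|
| 1 | 65.25 / 83.5 = 0.78 | 48 / 72 = 0.67 |
| 2 | 83.5 / 74.375 = 1.12 | 72 / 60 = 1.20 |
| 3 | 101.75 / 65.25 = 1.56 | 96 / 48 = 2.0 |

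The true rate ratio is 1 in every cell. If the 4 high-ADA patients fell at random among the 12, k = 2 would be the most likely of these cases: 210/495 = 42%, against 175/495 = 35% for k = 1 and 70/495 = 14% for k = 3.

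The n (%) column is affected too. At an assumed 0.2 events per year, the chance of at least one event, 1 − exp(−0.2 × years), is 33% at 2 years, 55% at 4 years and 86% at 10 years.

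**2. Events before the first sample at or above 12800**

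For a patient whose first such sample is at month T, with F months of follow-up and a constant rate, the share of TEAEs before it is T/F. Part of that time is the interval since the previous sample, when the titer may already have crossed. The brackets stop at the previous scheduled sample (month 0, 3, 9 or 21).

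| T (months) | F = 47 | F = 120 |
|---|---|---|
| 3 | 6.4% (0%) | 2.5% (0%) |
| 6 | 12.8% (6.4%) | 5% (2.5%) |
| 12 | 25.5% (19.1%) | 10% (7.5%) |
| 24 | 51.1% (44.7%) | 20% (17.5%) |

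A patient already at 12800 or more at study entry has a share near zero.

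**3. How finely the sampling can place an event**

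The longest interval between consecutive scheduled samples, with opposite use of the 60-day windows and none missed, is 91 + 60 + 60 = 211 days while sampling is 3-monthly, and 365 + 60 + 60 = 485 days once it is yearly.

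**The case against.** The strongest reply is that nothing formal depends on these tables. They are descriptive, there are 12 patients, and the SAP does not claim that antibodies cause events. AE listings, individual titer plots and per-patient exposure are all planned, so a careful reader can rebuild the order by hand. That stands, and it limits the severity. It does not make the columns comparable as printed, because the SAP plans no such reconstruction.

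Four further points stand:

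- **The labels classify patients.** A reader might infer that the SAP calls every TEAE in the column a high-antibody event. It does not; the table shows TEAEs in patients classed that way.
- **Misplaced time is not certain.** Patients could start alglucosidase alfa before entry and enrol up to 24 months of age, so some may already have been high at entry. How many had on-study time before a first high sample is unknown and could be none.
- **The final-sample effect is partly visible.** The peak-category table still shows such a patient at 12800 or more, provided that patient counts as seroconverted.
- **A before/after rate table would not settle the matter.** Split at 12800, it leaves seroconversion and the lower peak categories untouched. For patients who become high on study, the earlier part is also a younger age and a shorter treatment duration.

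**Conclusion.** The point holds as a minor one. The ADA-stratified TEAE tables cannot separate antibody level from length of follow-up, and they may include events that preceded the first high titer. On the stated assumptions, follow-up alone moves the ratio of TEAEs per patient from 1 to between 0.67 and 2.0 for 1 to 3 long-stayers among four high-ADA patients, with 1.12 or 1.20 in the central case. These figures illustrate possible size; they do not estimate what this study will show.

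A reader might go further and infer that the tables must overstate events under high antibody levels, or that a safety conclusion is invalid. The documents support neither. The distortion can run in either direction, the timing part may be nil, and no test, error rate or decision rule depends on these tables.

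**What to change.** In SAP 4.7.2, keep the planned tables and make three additions.

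1. **Person-time.** Give on-treatment patient-years and events per patient-year in every ADA column, using the SAP 4.1 on-treatment period so that numerator and denominator cover the same time. State that the numerator counts each episode, given the single-count rule.
2. **Footnote.** 'ADA labels are whole-study and not time-ordered.'
3. **TEAE listing.** For each event, show the last titer before onset, the days since that sample, and where onset falls: before the last sample below 12800 that precedes the first at or above it, in the gap between those two, or after the first sample at or above 12800. Mark patients who never reach 12800 and onsets too incomplete to place. State whether the baseline sample counts, because the SAP's peak starts at the first study infusion.

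A rate table split into those three parts is optional. If it is produced, note that it covers only the 12800 threshold and that its before/after comparison is confounded by age and treatment duration.

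The cost is SAP wording, a footnote and some programming on dates already collected. The limits are small cells and sampling gaps of up to 211 days (3-monthly) or 485 days (yearly), which will leave some events undetermined.

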4.7.3 Additional safety assessments

4.7.3.1 Laboratory variables, vital signs, physical examinations (PE), and electrocardiograms (ECGs)

The following laboratory variables, vital signs, physical examinations (PE), and electrocardiogram (ECG) variables will be analyzed.

- Hematology:
 - Complete blood count with differential
- Clinical chemistry:
 - Metabolism: glucose, total protein, albumin, creatine kinase (CK), creatine kinase MB (creatine kinase muscle, brain isoform [CK-MB]), creatine kinase MB/total creatine kinase
 - Electrolytes: sodium, potassium, chloride, calcium, phosphorus, bicarbonate
 - Renal function: creatinine, blood urea nitrogen (BUN), uric acid (urate)
 - Liver function: alanine aminotransferase (ALT) [serum glutamic pyruvic transaminase (SGPT)], aspartate aminotransferase (AST) [serum glutamic oxaloacetic transaminase (SGOT)], alkaline phosphatase, total bilirubin

- Urinalysis:
 - Urinalysis for quantitative analysis: urine appearance, specific gravity, pH, protein, glucose, ketones, bilirubin, and blood.
 - Microscopy will be performed if clinically indicated.
- Vital signs: heart rate, systolic and diastolic blood pressure, respiratory rate, and temperature
- PE body systems: General Appearance, Skin, HEENT, Lymph Nodes, Heart, Lungs, Breasts, Abdomen, External Genitalia, Pelvic, Rectal, Extremities/Joints, Neurological, Mental Status examinations
- 12-lead ECG variables:
 - Intervals and measurements: heart rate, RR, PR, QRS duration, QRS axis, QT, QTc (Bazett and Fridericia correction)
 - Findings: sinus rhythm, LVH, RVH, conduction abnormalities

For summary tables, data below the lower limit of quantitation/detection limit (LLOQ) will be replaced by half of the LLOQ, while data above the upper limit of quantification (ULOQ) will be replaced by ULOQ value.

Analyses of quantitative variables

For all laboratory variables and quantitative ECG variables (intervals and measurements) above, descriptive statistics for results and changes from baseline will be provided for each planned visit during the on-treatment period. Vital signs data will be provided in a listing.

PE findings

PE findings (normal, abnormal, not examined) for each body system will be presented in a listing.

Analyses of ECG findings

For ECG, the incidence of patients with at least one abnormal ECG during the treatment-emergent period will be summarized according to the following baseline status categories:

- Normal/missing
- Abnormal

Analyses according to PCSA

Potentially clinically significant abnormality (PCSA) analyses will be performed based on the PCSA criteria defined in Sanofi business and technical document BTD-009536, in effect at Sanofi at the time of the database lock.

Analyses according to PCSA will be performed based on the worst value during the treatment-emergent period, using all measurements (whether local or central, scheduled, nonscheduled or repeated).

For laboratory variables, vital signs, and ECG variables (intervals and measurements) above, the incidence of patients with at least one PCSA during the treatment-emergent period will be summarized regardless of the baseline level.

4.7.3.2 *Neuroimaging Assessment*

As described in protocol Section 9.3.1, serial brain MRIs will be conducted at the discretion of the Investigator as sedation for this procedure may be required for young patients and may pose an unacceptable risk in patients who have cardiopulmonary involvement. MRIs will be conducted according to standard procedures (specified in the study manual [SM]) at the times specified in protocol Table 9-1 in order to evaluate possible changes in brain structures over time.

Neuroimaging assessments will be presented in a listing.

4.7.3.3 *Hearing Testing*

As described in protocol Section 9.3.2, hearing will be assessed at the times specified in protocol Table 9-1 using an age-appropriate method of hearing assessment, as determined by the Investigator.

Hearing testing results will be presented in a listing.

4.7.3.4 *Visual Screening*

Ophthalmologic evaluation is to be performed by the Investigator in accordance with the guidelines described by the American Association of Pediatrics (AAP, 1996, *Pediatrics*). The type of visual screening will be determined by the patient's age at the time of the assessment. All patients will have an exam of the eye, test ocular motility and the red reflex exam. Patients 3 years of age and over will have the same assessments described previously plus a visual acuity test. Patients 4 years of age and over will have each of the previously described assessments plus fundoscopy.

Visual screening results will be presented in a listing.

